4.2.8. Oxidative stress markers. Markers of oxidative stress are increased in patients with ESRD⁵³⁻⁵⁵ and associated with increased mortality.^{56,57} Treatment with the antioxidant alpha tocopherol has been reported in a small study to decrease mortality.⁵⁸ Chronic exercise training can reduce oxidant stress and may be one mechanism whereby exercise improves cardiovascular outcomes.^{59,60} To determine whether EMS alters markers of oxidative stress we will measure serum F2-isoprostane (a measure of lipid oxidation), protein thiols (a measure of protein oxidation) and the ratio of reduced to oxidized glutathione (GSH/GSSG) in erythrocytes.⁶¹⁻⁶³ To assess the effect of EMS on antioxidant levels we will measure erythrocyte glutathione peroxidase (GPx), superoxide dismutase (SOD) and catalase (CAT) activity.⁶⁴ These markers will be measured at 5 time points: baseline, pre-EMS, after 8 and 16 weeks of EMS training and 4-weeks after completion of EMS training.

4.2.9. Anemia is a marker of inflammation⁶⁵ and associated with morbidity and mortality in dialysis patients.^{66,67} The blood levels of hemoglobin, iron saturation and ferritin, as well as the dose of erythropoietin and iron administered are tracked monthly as routine standard of care for hemodialysis patients. We will collect each of these variables from the patient chart starting with the labs drawn just before enrollment and continuing through labs drawn 4 weeks after completing the EMS training. We will plot this data to see whether any change occurred during treatment with EMS.

4.2.10. Serum phosphorus is associated with mortality for hemodialysis patients.⁶⁸ Control of phosphorus levels using phosphate binders taken 3 times a day with meals is one of the major causes of excessive pill burden for these patients.³¹ EMS has been shown to increase intra-dialytic phosphate removal and may help lower serum phosphate or reduce pill burden for these patients.²⁹ Serum phosphorus, calcium, and PTH as well as dose of phosphate binders prescribed are recorded monthly for hemodialysis patients as part of standard of care. We will collect each of these variables from the patient chart starting with the labs drawn just before enrollment and continuing through labs drawn 1 month after completing the EMS training. We will plot this data to see whether any change occurred during treatment with EMS.

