treatment and after 8 and 16 weeks of EMS training to determine the chronic effect of EMS training on muscle gene expression. Gene expression analysis will be done using Affymetrix Human Exon 1.0 ST arrays as previously described.⁷⁰ We will first examine specific genes that are highly overexpressed or under-expressed after acute and chronic exercise compared to the baseline (pre-EMS). We will also look for biological pathways activated or suppressed by acute and chronic exercise specifically looking at pathways relating to muscle glucose metabolism and insulin response, mitochondrial biogenesis and function, muscle phenotype, growth and energy metabolism, oxidant stress and inflammation. A future goal of this research is to compare the gene expression response to EMS in this study with that seen in patients with normal renal function and varying levels of CKD to see if the gene response profile is qualitatively different in patients with varying levels of kidney function. We are also interested how the gene expression profiles seen with EMS compare to that seen with traditional volitional aerobic exercise to determine if EMS activates different genes or biological pathways than volitional exercise.

5. Visits & Assessments.

Patients will be identified from the population of patients on regular maintenance hemodialysis at one of the University of Iowa dialysis units. Potential subjects will be approached at a dialysis visit and informed of the study.

5.1. Visit 1. If they indicate an interest in participating we will proceed with obtaining written informed consent and confirm that they meet all the inclusion criteria and none of the exclusion criteria.

- Obtain informed consent to participate and consent to access additional appropriate medical records
- Review inclusion and exclusion criteria

Baseline data collection (Day -35 to -28). Performed at dialysis unit or CRU as appropriate. Up to 4 hours time.

- Record demographics and baseline disease characteristics
- Record past medical history and current review of symptoms
- Record current dialysis orders
- Record episodes of dialysis hypotension (SBP<90 or symptoms needing saline, last 6 HD sessions)
- Record baseline exercise status (minutes of exercise per week)
- Record concomitant medications
- Malnutrition-inflammation (MIS) assessment
- Kidney Disease Quality of Life-36 (KDQOL-36) assessment
- Patient Health Questionnaire-9 (PHQ-9)
- Record sitting blood pressure and pulse

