- Physical examination by a physician
- 6-minute walk test
- Record height, weight, waist circumference, hip circumference
- Thigh circumference bilaterally
- Record most recent standard dialysis monthly lab tests.
 - o Monthly labs (predialysis): albumin, alkaline phosphatase, bicarbonate, blood urea nitrogen, calcium, chloride, complete blood count, creatinine, iron studies, ferritin, hemoglobin A1c (if available), phosphorus, potassium, sodium, total protein, 25 hydroxy vitamin D. eGFR calculation by modified MDRD equation from enzymatic creatinine determination)
 - o Monthly labs (postdialysis): blood urea nitrogen. Calculated urea reduction ratio from pre and

post dialysis BUN.

- Fasting blood sample (30 ml) for:
 - o Insulin and glucose
 - o Interleukin-6 (IL-6), tumor necrosis factor alpha (TNF α), C-reactive protein
 - o Glutathione (reduced and oxidized forms), glutathione peroxidase (GPx), superoxide dismutase (SOD), catalase (CAT), F2 isoprostane and protein thiols.
- Measure quadriceps muscle strength (bilaterally)
- 48 hour activity monitoring (using wrist watch monitor between dialysis sessions).

5.2. Visit 2. Pre-EMS training data collection (Day -7 to 0). Performed at dialysis unit or CRU where specified. Time required up to 4 hours.

- Record any new medical conditions, symptoms or complaints
- Record current dialysis orders
- Record episodes of dialysis hypotension (SBP<90 or symptoms needing saline, last 6 HD sessions)
- Record current exercise status (minutes of exercise per week)
- Record concomitant medications
- Malnutrition-inflammation (MIS) assessment
- Kidney Disease Quality of Life-36 (KDQOL-36) assessment
- Patient Health Questionnaire-9 (PHQ-9)
- Record vital sign measurements (predialysis or non-dialysis day, same timing as baseline measures)
- 6-minute walk test
- Record weight, waist circumference, hip circumference
- Thigh circumference bilaterally
- Record most recent dialysis monthly lab tests. (Drawn no more than 7 days prior to optimization visit)
 - o Monthly labs (predialysis): albumin, alkaline phosphatase, bicarbonate, blood urea nitrogen, calcium, chloride, complete blood count, creatinine, iron studies, ferritin, hemoglobin A1c (if available), phosphorus, potassium, sodium, total protein, 25 hydroxy vitamin D. eGFR calculation by modified MDRD equation from enzymatic creatinine determination)
 - o Monthly labs (postdialysis): blood urea nitrogen. Calculated urea reduction ratio from pre and post dialysis BUN.

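### The monthly anemia and phosphorus chart series start too late to show a patient's usual variation or an existing trend before EMS

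*Combined protocol and SAP*

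**What the plan says.** Section 4.2.9 lists hemoglobin, iron saturation, ferritin and the erythropoietin and iron doses, which "are tracked monthly as routine standard of care for hemodialysis patients". They are collected "from the patient chart starting with the labs drawn just before enrollment and continuing through labs drawn 4 weeks after completing the EMS training". Section 4.2.10 does the same for phosphorus, calcium, PTH and binder dose: "starting with the labs drawn just before enrollment and continuing through labs drawn 1 month after completing the EMS training". Both sections end with the same statement of analysis: "We will plot this data to see whether any change occurred during treatment with EMS". Neither defines a change, gives a threshold or states a within-patient SD.

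Section 5.1 puts enrollment and baseline at Day -35 to -28, and section 5.2 puts the pre-EMS visit at Day -7 to 0. Between them lies the 4-week care-optimization phase (section C.1). Its goals in Table 1 cover hemoglobin, iron saturation, calcium, phosphate and PTH. All patients then receive 16 weeks of EMS, with no comparison group. Section 8 says that changes over time in the outcome variables will be tested by Friedman's method at P<0.05. Section 5.1 also obtains "consent to access additional appropriate medical records".

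**The concern.** Without a control group, a patient's course before EMS is the main evidence of what would have happened anyway. Two monthly values give almost no information on usual spread, and a line through two points has no error estimate, so an existing trend cannot be recognized. The two values also lie on either side of a deliberate change in care aimed at most of the plotted labs, so only about one of them describes optimized care before EMS.

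The risk is that ordinary fluctuation, or a drift that began before enrollment, is reported as an effect of EMS on anemia, mineral markers or drug dose. Section 8 gives the pilot the task of estimating both change and variability in the secondary outcomes for a larger trial. A two-value lead-in serves that aim poorly. Blood pressure is better placed: section 4.2.11 averages session readings over the whole 4-week optimization phase, about 3 x 4 = 12 sessions.

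**Working it through.** **The plan's own figure.** None is given for these series. The only power statement (section 8) concerns HOMA-IR. It reproduces: difference 0.28 x 4.8 = 1.344, SD of the paired difference taken as 1.7, n = 15, two-sided 5% t-test, power 81.2% against the stated 80%. It has no bearing on the chart series.

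**Step 1: number of values.** Inputs are enrollment on Day -35 to -28, a first value from the last draw before enrollment, EMS from Day 0 to Day 112, and a monthly cycle taken as 28, 30 or 31 days (assumption). Counting draws over every enrollment day and every position in the cycle gives:

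| Cycle (days) | 1 pre-EMS | 2 pre-EMS | 3 pre-EMS | Values during EMS |
|---|---|---|---|---|
| 28 | 0% | 87.5% | 12.5% | 4 |
| 30 | 1.3% | 92.5% | 6.2% | 3 or 4 |
| 31 | 2.4% | 93.5% | 4.0% | 3 or 4 |

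Two pre-EMS values is therefore the normal case. Section 5.2 wants the second drawn within 7 days of what it calls the optimization visit. Read as Visit 2, that dates it to between Day -14 and Day 0, late in the optimization phase or at its end.

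**Step 2: chance of an apparent change when nothing changes.** Take 2 pre-EMS and 4 EMS values, independent with a constant mean; the rules that use means also assume normality. The documents state no reading rule, so several are shown.

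- *Any EMS value outside the pre-EMS range:* 1 - (2 x 1)/(6 x 5) = 93.3%.
- *EMS mean outside the pre-EMS range:* EMS mean minus one earlier value has variance 1 + 1/4 = 1.25. Two such differences share variance 1/4, so their correlation is 0.25/1.25 = 0.2. The probability is 2 x [1/4 + arcsin(0.2)/(2π)] = 56.4%.
- *Means differ by more than 1 within-patient SD:* SD of the difference is sqrt(1/2 + 1/4) = 0.866; 2 x [1 - Φ(1/0.866)] = 24.8%.
- *All four EMS values beyond both earlier ones on the same side:* 2/C(6,2) = 2/15 = 13.3%.
- *Two-sample t-test at 5%:* 5%.

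With month-to-month correlation of 0.3 to 0.6 (simulation, 400,000 series), these become 95-97%, 64-72%, 28-29%, 20-28% and 9-14%.

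**Step 3: what earlier months can and cannot add.** Six earlier months bring the lead-in to 8 values. If all 8 are treated as one stable series, the EMS mean falls outside their range in 6% of patients (27% at correlation 0.7). This does not measure the benefit of the fix, because seven of the eight values precede optimization. With a 1 SD shift caused by optimization (assumption) and no EMS effect, the 8-value rule flags 21%. Measured against the single post-optimization value, the change has SD sqrt(1 + 1/4) = 1.12 within-patient SD, with or without the extra months. What the extra months do supply is an estimate of spread and slope: for 8 independent monthly points the slope has SE 1/sqrt(42) = 0.154 SD per month.

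**The case against.** **The frequency depends on the rule.** A reader might infer that ordinary variation will look like a change in most patients. The documents do not support that. They describe a plot with no rule and no SD, and the rates in step 2 run from 5% to 93% according to how the plot is read.

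**A group test may apply.** Both series are secondary outcomes, so section 8 can fairly be read as applying Friedman's test to them. With 15 patients and no change over time, its simulated false-positive rate is about 4.5%. That stands, but only under that null. The test asks whether values differ across time points. It cannot tell an EMS effect from a drift already under way or from a shift produced by optimization, whereas section 8 reads a significant result as an effect of EMS.

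**There is a value after EMS.** Both series run to about a month after stopping, which allows some check for reversal. This helps, but it is about one value per patient and does not show the course before EMS.

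**The longer series has limits.** A reader might also infer that it would cut false changes from 56% to 6%. It would not: that figure pools months under different care (step 3). Nor is it certain that every chart holds six earlier months, since section 3.1 sets no minimum prior time on dialysis.

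**Proportion.** Most secondary outcomes use the same two-point baseline, and this is a pilot of up to 15 patients. That argues for a low grade. It does not argue against the change, because here earlier values may already exist in the chart.

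**Conclusion.** The point holds in a limited form. Starting with the draw just before enrollment leaves about two pre-EMS values per patient, one on each side of care optimization. A single-arm plot built on them cannot show usual spread or a prior trend, so variation or drift can be mistaken for an EMS effect. The per-patient chance has no single value: 56% if the EMS mean is compared with the pre-EMS range, 5% to 25% under the stricter rules. These figures assume a constant mean, independent months and, where means are used, normality; serial correlation raises them. The count of values assumes a 28 to 31 day lab cycle. This is a minor matter and a cheap improvement, affecting secondary descriptive outcomes only.

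**What to change.** In 4.2.9 and 4.2.10, replace the start-point clause with: *starting with the monthly labs and doses recorded up to 6 months before enrollment, where available*. Align the Visit 1 chart item in 5.1, which asks only for the most recent monthly labs. Then state that:

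- enrollment, EMS start and EMS stop are marked on each plot;
- the earlier months are used only to show usual spread and prior trend;
- the post-optimization value remains the reference level for change during EMS;
- a change that continues a pre-enrollment trend is not attributed to EMS.

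The cost is a short wording and data-form change, plus abstraction of about six monthly lab sets for each of up to 15 patients (at most 6 x 15 = 90 sets). No visit or blood draw is added, and section 5.1 already takes consent for record access. Earlier months may be missing for recent dialysis starters. Because they precede optimization, they cannot separate its effect from that of EMS.

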- Fasting blood sample (30 ml) for:
 - o Insulin and glucose
 - o Interleukin-6 (IL-6), tumor necrosis factor alpha (TNF α), C-reactive protein
 - o Glutathione (reduced and oxidized forms), glutathione peroxidase (GPx), superoxide dismutase (SOD), catalase (CAT), F2 isoprostane and protein thiols.
- Measure quadriceps muscle strength (bilaterally)
- 48 hour activity monitoring (using wrist watch monitor between dialysis sessions).
- DXA scan (performed in CRU)

- Perform exercise stress test to determine peak VO₂ (performed in CRU)

5.3 Visit 3. Initiate EMS training (Day 0). Performed in dialysis unit and CRU. 60-75 minutes. 30 minutes extra for optional muscle biopsy, if performed.

- Perform pre-EMS muscle biopsy before starting dialysis (optional)
- EMS training is done while on hemodialysis starting approximately 30 min after dialysis initiation.
 - o Record pre-EMS blood pressure and pulse
 - o Initiate EMS training on quadriceps muscle of leg not used for muscle biopsy for 15 minutes while on dialysis
 - o Measure and record BP and pulse before and just prior to completion of EMS training.
 - o Record any symptoms related to EMS
 - o Train patient how to use EMS device.

5.4 . Visits 4-8, 11. EMS training visits (Day 2/3 and 7). Performed in dialysis unit. Time required up to 45 minutes.

- Record any new medical conditions, symptoms or complaints
- Observe patient initiate and perform EMS training.
 - o Adjust stimulus intensity to maximum tolerated by patient for both legs
- Record EMS setting used.
- Record pre-dialysis sitting BP and pulse
- Record post-dialysis sitting BP and pulse

5.5 Visits 9 &12. Outcome assessment visits (Day 56 & 112 ± 7 days). Performed in dialysis unit or CRU where specified. Time required up to 4 hours.

- Record any new medical conditions, symptoms or complaints
- Record current dialysis orders
- Record episodes of dialysis hypotension (SBP<90 or symptoms needing saline, last 6 HD sessions)
- Record current exercise status (minutes of exercise per week)
- Record concomitant medications
- Malnutrition-inflammation (MIS) assessment
- Kidney Disease Quality of Life-36 (KDQOL-36) assessment
- Patient Health Questionnaire-9 (PHQ-9)
- Record vital sign measurements (predialysis or non-dialysis day, same timing as baseline measures)
- 6-minute walk test
- Record weight, waist circumference, hip circumference
- Record thigh circumference bilaterally
- Record most recent dialysis monthly lab tests.

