 - o Monthly labs (predialysis): albumin, alkaline phosphatase, bicarbonate, blood urea nitrogen, calcium, chloride, complete blood count, creatinine, iron studies, ferritin, hemoglobin A1c (if available), phosphorus, potassium, sodium, total protein, 25 hydroxy vitamin D. eGFR calculation by modified MDRD equation from enzymatic creatinine determination)

- o Monthly labs (postdialysis): blood urea nitrogen. Calculated urea reduction ratio from pre and post dialysis BUN.
- DXA scan (performed in CRU)
- Measure quadriceps muscle strength (bilaterally)
- Perform exercise stress test to determine peak VO_2 (performed in CRU)
- 48 hour activity monitoring (using wrist watch monitor between dialysis sessions).

5. 6 Visits 10 & 13 Outcome assessment visits (Day 56 & 112 ± 7 days).

- Fasting blood sample (30 ml) for:
 - o Insulin and glucose
 - o Interleukin-6 (IL-6), tumor necrosis factor alpha (TNF α), C-reactive protein
 - o Glutathione (reduced and oxidized forms), glutathione peroxidase (GPx), superoxide dismutase (SOD), catalase (CAT), F2 isoprostane, protein thiols.
- Muscle biopsy (optional)

5.7. Visit 14. Post-EMS visit (Day 142 - 149). Performed in dialysis unit. Time required 2-3 hours.

- Record any new medical conditions, symptoms or complaints
- Record current dialysis orders
- Record episodes of dialysis hypotension (SBP<90 or symptoms needing saline, last 6 HD sessions)
- Record current exercise status (minutes of exercise per week)
- Record concomitant medications
- Malnutrition-inflammation (MIS) assessment
- Kidney Disease Quality of Life-36 (KDQOL-36) assessment
- Patient Health Questionnaire-9 (PHQ-9)
- Record vital sign measurements (predialysis or non-dialysis day, same timing as baseline measures)
- 6-minute walk test
- Record weight, waist circumference, hip circumference
- Record thigh circumference bilaterally
- Record most recent dialysis monthly lab tests. (Drawn no more than 7 days prior to optimization visit)
 - o Monthly labs (predialysis): albumin, alkaline phosphatase, bicarbonate, blood urea nitrogen, calcium, chloride, complete blood count, creatinine, iron studies, ferritin, hemoglobin A1c (if available), phosphorus, potassium, sodium, total protein, 25-hydroxy vitamin D. eGFR calculation by modified MDRD equation from enzymatic creatinine determination)
 - o Monthly labs (postdialysis): blood urea nitrogen. Calculated urea reduction ratio from pre and post dialysis BUN.
- Fasting blood sample (30 ml) for:

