9.1. HOMA-IR and leptin-adiponectin ratio (LAR). HOMA-IR and LAR are both separate measures of insulin resistance. Patients will fast for 12 hours and withhold taking their morning insulin or oral antidiabetic agents prior to the test. Venous blood (10 ml) will be drawn into a red top tube (serum separator) placed on ice and centrifuged at 3,000 rpm at 4°C to separate serum. The serum is aliquoted and stored at -80°C until assay. Fasting serum insulin (μ U/ml) is measured using an electrochemiluminescent assay and fasting serum glucose (mg/dl) by a hexokinase assay in the UIHC clinical chemistry lab. HOMA-IR score is calculated using the homeostatic model assessment equation (HOMA-IR = fasting glucose (mg/dl) x fasting Insulin (μ U/mL) / 405). Serum leptin (ng/ml) and adiponectin (ng/ml) are measured by RIA using Linco kits (Linco, St. Charles, MO) in [name] lab at Iowa.

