In Affymetrix Human Exon 1.0 ST arrays, the log2 hybridization signal reflects the mean signal intensity of all exon probes specific for an individual mRNA, and is proportional to the level of that mRNA. We will perform two main comparisons: 1) the effect of acute exercise comparing the gene expression levels 4 hours after the first EMS training to baseline before training and 2) the effect of chronic EMS training (8 and 16 weeks) compared to the Pre-EMS training sample. We will restrict the analysis to mRNA's that have a mean log2 hybridization signal of >5 in either the pre-EMS sample or the 8 or 16 week EMS treatment conditions. We will use paired t-tests to determine which of the remaining mRNA's are present at a significantly different level (adjusting for the false discovery rate inherent in multiple testing) in the EMS treatment compared to the baseline sample. The list of differentially expressed genes will be examined for important biological pathways relating to muscle glucose metabolism and insulin response, mitochondrial biogenesis and function, muscle phenotype, growth and energy metabolism, oxidant stress and inflammation. We will also use bioinformatics tools such as Onto-Express to help translate the list of differentially expressed genes into functional categories such as biological process or cellular role based on the annotation using Gene Ontology terms. All microarray data will be deposited in the GEO database.

10. References

1. U.S. Renal Data System, *USRDS 2012 Annual Data report: Atlas of End-Stage Renal Disease in the United States*, National Institutes of Health, National Institute of Diabetes and Digestive and Kidney Diseases, Bethesda, MD, . 2012.
2. Carrero JJ, de Jager DJ, Verduijn M, et al. Cardiovascular and noncardiovascular mortality among men and women starting dialysis. *Clin J Am Soc Nephrol*. Jul 2011;6(7):1722-1730.
5. Johansen KL. Exercise in the end-stage renal disease population. *J Am Soc Nephrol*. Jun 2007;18(6):1845-1854.

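### Food and glucose-drug state is not matched across biopsies: the week 8 and 16 biopsies share the fasting-draw visit and the pre-EMS biopsy does not, so the chronic-training gene contrast can mix fasting with EMS effects

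*Combined protocol and SAP*

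**What the plan says.** Baseline biopsy: section 5.3 (Visit 3, Day 0) lists "Perform pre-EMS muscle biopsy before starting dialysis (optional"). Nothing else in that visit calls for a blood draw, a fast or withheld drugs. The pre-EMS fasting sample belongs to section 5.2, "Visit 2. Pre-EMS training data collection (Day -7 to 0").

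Later biopsies: section 5.6, "Visits 10 & 13 Outcome assessment visits (Day 56 & 112 ± 7 days"), has two items only, "Fasting blood sample (30 ml) for" insulin, glucose and other markers, and "Muscle biopsy (optional").

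Conditions of the fasting draw: section 9.1 states "Patients will fast for 12 hours and withhold taking their morning insulin or oral antidiabetic agents prior to the test". Sections 4.2.12 and 9.7, which describe the biopsies, set no food or drug condition for any of them.

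Use of the samples: section 9.8 names as its second main comparison "the effect of chronic EMS training (8 and 16 weeks) compared to the Pre-EMS training sample", tested gene by gene with paired t-tests and a false discovery rate adjustment. Section 4.2.12 says the pathway work will be "specifically looking at pathways relating to muscle glucose metabolism and insulin response", with energy metabolism also on the list.

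**The concern.** Every patient receives EMS, so the chronic-training contrast is purely before against after. Any condition that changes between the first and later biopsies for a reason other than training is attributed to training. The visit lists build in one such condition: the later biopsies share a visit with a 12-hour fast, and the first does not.

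The glucose, insulin and energy pathways that the protocol singles out are the ones where recent food and insulin would be expected to matter. False discovery rate control limits chance findings. It does nothing about a real expression difference that has another cause.

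The data are to be deposited in GEO, and comparison with other kidney-function groups and with volitional exercise is a stated future goal, so a mixed signal would carry forward. Without a record of food and drug state, nobody could later tell which pairs were comparable.

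**Working it through.** **Step 1. The plan's own figure.** Section 8 has one power statement: 15 patients, HOMA-IR 4.8 (SD 1.7), a 28% decrease, 80% power, paired t-test at 0.05. The decrease is 0.28 × 4.8 = 1.344. Taking 1.7 as the SD of the paired difference, the standardised effect is 1.344 / 1.7 = 0.79, and exact two-sided power (noncentral t, 14 df) is 81.2%. The figure reproduces, but it concerns HOMA-IR. The gene-expression analysis has no sizing of its own, and the present point does not depend on this figure.

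**Step 2. The visits side by side.**

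| | Pre-EMS | Weeks 8 and 16 |
|---|---|---|
| Biopsy | Visit 3, Day 0 (5.3) | Visits 10 and 13 (5.6) |
| Fasting draw | Visit 2, Day -7 to 0 (5.2) | Visits 10 and 13 (5.6) |
| Same visit? | No | Yes |
| Fast and drug withholding attached to the biopsy visit | None stated | Yes, through the draw (9.1) |
| Biopsy timing relative to dialysis | Before dialysis | Not stated |

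Section 1 of the Approach keeps the later biopsies off the stress-test day. At weeks 8 and 16 the draw and the biopsy were both separated from the main assessment visit; at baseline only the biopsy was. The mismatch looks like a by-product of scheduling, and no section justifies it.

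**Step 3. What the contrast estimates.** For one gene, the mean paired difference is (EMS effect) + π × (fasting effect), where π is the share of pairs fasted later but not at baseline. More pairs narrow the interval around that sum without removing the second term.

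**Step 4. Illustrative size.** The documents give no fasting effect, no share of responsive genes, no false discovery rate level and no expected number of biopsied patients. All four are assumed here: zero EMS effect, 5% of genes responsive, Benjamini-Hochberg at 5%, and π = 1. Section 9.8 gives more than 17,000 transcripts. Using 17,000 ignores the signal filter, and 0.05 × 17,000 = 850 genes are shifted. Each gene gets a paired t-test with n - 1 df and noncentrality s√n, where s is the shift in SDs of the paired difference. Share of the 850 that reach the list (10 simulated data sets per cell):

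| Shift | 6 pairs | 10 pairs | 15 pairs |
|---|---|---|---|
| 0.5 SD | 0% | 0% | 0% |
| 1.0 SD | 0% | 3% | 45% |
| 1.5 SD | 0.2% | 62% | 96% |
| 2.0 SD | 9% | 95% | 99.9% |

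With no shift, essentially nothing is listed.

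A second simulation assumed 10,000 genes after filtering, 500 of them responsive (100 data sets per cell). At 1.0 SD it lists on average about 14 genes with 10 pairs and about 250 with 15. At 1.5 SD it lists about 325 and 507. These counts include a few unshifted genes.

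**Step 5. Relaxing the assumptions, at 1.0 SD and 10,000 genes.** If each patient is discordant with probability 50%, the mean list falls to about 0.05 genes with 10 pairs and about 1 with 15. If only 1% of genes respond, it is 0.6 and 17. With 6 or 8 pairs and the other assumptions unchanged, it is 0.3 and 1.1.

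**The case against.** A reader might infer that every biopsied patient is fed and medicated at baseline and fasted with drugs withheld later, so that the resulting list is simply a list of fasting genes. The documents do not support that.

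- Section 5.3 is silent on food. It does not say that patients have eaten, and a patient dialysed in the morning may not have.
- The Visit 2 window reaches Day 0, so the fasting draw and the baseline biopsy could fall on the same day.
- Section 5.6 does not place the biopsy before the next meal or dose. The fast in section 9.1 is tied to the blood test, and section 6.3 has blood drawn from the dialysis needle.
- Drug withholding concerns only patients on insulin or oral agents. Diabetes is neither required nor excluded.
- Biopsies are optional within a maximum of 15 patients, so 15 pairs is a ceiling, and with few pairs or a modest shift the expected false list is close to empty.
- Figure 1, the visit diagram, was not available in the text reviewed, so any biopsy condition stated there could not be checked.

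All of this stands, and it lowers the certainty and the likely size. It does not remove the point. Silence at Visit 3 and an unfixed order at Visits 10 and 13 leave metabolic state uncontrolled, while the visit lists still push it in one direction. Elsewhere the protocol accepts the principle of matched conditions: vital signs are to be taken at the same timing as at baseline, and the study blood sample is fasting at all five time points.

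**Conclusion.** The point holds as a likely mismatch in the visit schedule. Biopsies are not matched for food and glucose-drug state. If the lists are followed, the later ones are likely to be fasted and the baseline one need not be, so the uncontrolled section 9.8 contrast can credit EMS with fasting-responsive genes. It is not certain in any given patient.

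The size cannot be derived from the documents. Under the stated assumptions it ranges from almost nothing (0.5 SD at any feasible number of pairs, or 6 pairs at 1.0 SD) to most fasting-responsive genes (62% to 96% at 1.5 SD with 10 to 15 pairs). The upper end needs a large shift, at least about 10 biopsied patients and near-universal discordance together.

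The reach is limited to one optional secondary outcome in a pilot. HOMA-IR comes from a fasting sample at all five time points and is unaffected. The change is still worth making, because it is cheap and samples cannot be matched after collection.

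**What to change.** Reconcile sections 5.3, 5.6, 9.1 and 9.7 so that all biopsies of a patient are taken in the same food and glucose-drug state. Either pair every biopsy with a fasting draw or pair none of them; which state to use is for the investigators. State the order of biopsy, draw, next meal or dose, and dialysis at Visits 10 and 13, as section 5.3 already does for dialysis at Visit 3.

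At each biopsy, record the time since the last meal and since the last insulin or oral agent. In section 9.8, report how many pairs are discordant and take this into account when interpreting the chronic-training contrast, above all for the glucose, insulin and energy pathways. Repeating the analysis on matched pairs alone need not be mandatory, since it could leave very few pairs.

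Cost: protocol wording, two extra recorded times per biopsy, and a different dialysis day for some biopsies. No extra biopsy and no extra patient.
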